4.6 Subject Replacement Strategy

If a subject discontinues from study drug or withdraws from the study, a replacement subject may be enrolled if deemed appropriate by the investigator and Sponsor. The replacement subject will generally receive the same study drug as the subject being replaced. The replacement subject will be assigned a unique screening/randomization number.

5 TREATMENTS

5.1 Investigational Study Drug

5.1.1 Description

PT101 is a recombinant mutant form of human IL-2 fused at its C-terminus to an effector function ablated human IgG1 Fc domain. ^{CCI}

CCI

Placebo is similar in color and presentation to PT101 to ensure blinding is maintained but will contain no active ingredients. Placebo will be administered as 5% dextrose or 5% D-glucose

sourced by the investigative site. All study drug (PT101 and placebo) is stored per storage conditions written on the label.

5.1.2 Dose and Administration

CCI
CCI [REDACTED] administered by SC injection. Additional dose levels or regimens of PT101 to be evaluated in the optional cohorts will be determined by the DRC following cumulative review of available safety, PK, PD, measures of UC disease activity, and biomarker data.

On visit days where the study drug is being administered, all safety, PK, and PD procedures are to be conducted before administration of study drug, unless otherwise specified CCI

5.1.3 Storage and Handling

Upon receipt, PT101 should be visually inspected and then stored per storage conditions written on the label in a secured location accessible only to authorized study staff.

5.1.4 Packaging and Labeling

Packaging and labelling will be in accordance with applicable local regulatory requirements and applicable Good Manufacturing Practice guidelines. PT101 will be packed in boxes containing a suitable number of vials. The information on the boxes and vials will be in accordance with approved submission documents.

5.1.5 Preparation

Study drug will be prepared and dispensed by the unblinded HCP according to the instructions in the Pharmacy Manual. PT101 must be administered within 4 hours from the time the vial seal was opened. Placebo will be 5% dextrose or 5% D-glucose, which will be provided by the investigative site.

Source documentation will be maintained by both the unblinded HCP and site staff on both the preparation and administration of study drug.

The Investigator, or a qualified designee, will administer study drug according to the instructions in the Pharmacy Manual.

5.2 Concomitant Therapy

All concomitant medications administered will be recorded from randomization through the safety reporting period. Any concomitant medication given for AEs that are the result of a study protocol-specified intervention should be recorded from the time of informed consent.

5.2.1 Vaccine Guidelines

Prior to study participation, it is recommended that the subject's vaccinations be brought up to date according to local vaccination standards.

Inactivated vaccines (such as inactivated influenza vaccines) should be administered according to local vaccination standards whenever medically appropriate; however, there are no available data on the concurrent use of PT101 and its impact on immune responses following vaccination.

Live or attenuated vaccines (including, but not limited to varicella, measles, mumps, and rubella [MMR], MMR plus varicella [MMRV], live attenuated influenza vaccine [LAIV], yellow fever, Ty21a oral typhoid, bacille Calmette-Guerin [BCG], smallpox, and rotavirus) are prohibited within 4 weeks of screening, throughout the study, and for 12 weeks after the last dose of study drug.

Regarding precautions related to the vaccination of household or close contacts, subjects participating in this study are recommended to follow country-specific guidelines or those of the US Centers for Disease Control regarding contacts as appropriate (<https://www.cdc.gov/vaccines/hcp/acip-recs/general-recs/immunocompetence.html>). In general, household contacts and other close contacts of subjects in this trial may receive all age- and exposure-appropriate vaccines.

5.2.2 Prohibited Concomitant Therapy

Some medications and treatments may have an impact on the safety of the subjects and/or efficacy assessments of this study. Prohibited concomitant medications that may impact efficacy assessments or impact subject safety are presented in [Table 1](#). Subjects who initiate any of these concomitant medications at any time during the IBT phase of the study must be discontinued from study drug and will not be eligible for the OL or CBT phase of the study. Subjects who initiate any of these concomitant medications at any time during the OL or CBT phase of the study must be discontinued from study drug.

Medications or vaccinations specifically prohibited in the exclusion criteria and in [Table 1](#) are not allowed during the ongoing study. If there is a clinical indication for any medications or vaccinations specifically prohibited (i.e., as supportive care or to treat AEs as deemed necessary by the investigator or the subject's physician), discontinuation from study drug may be required. The investigator should discuss any questions regarding this with the Medical Monitor. The final decision on any supportive therapy or vaccination rests with the investigator and/or the subject's primary physician. However, the decision to continue the subject on study drug requires the mutual agreement of the investigator, the Sponsor, and the subject.

Table 1: Prohibited Concomitant Medications that May Impact Efficacy Assessments or Impact Subject Safety

Drug Class	Agents Disallowed	Prohibited Period
TNF α antagonist	Infliximab (t $\frac{1}{2}$: 9.5 days) Adalimumab (t $\frac{1}{2}$: 10-20 days) Golimumab (t $\frac{1}{2}$: 12-14 days) Certolizumab (t $\frac{1}{2}$: 14 days)	5 half-lives prior to Day 1* through the end of treatment
Integrin antagonist	Vedolizumab (t $\frac{1}{2}$: 25 days) Natalizumab (t $\frac{1}{2}$: 11 days)	5 half-lives prior to Day 1* through the end of treatment
Interleukin antagonist	Ustekinumab (t $\frac{1}{2}$: 19 days)	5 half-lives prior to Day 1* through the end of treatment
JAK inhibitor	Baricitinib (t $\frac{1}{2}$: 12 hours) Tofacitinib (t $\frac{1}{2}$: 3 hours) Tofacitinib XR (t $\frac{1}{2}$: 6-8 hours) Upadacitinib (t $\frac{1}{2}$: 8-14 hours)	5 half-lives prior to Day 1* through the end of treatment
S1P1 inhibitor	Fingolimod (t $\frac{1}{2}$: 6-9 days) Ozanimod (t $\frac{1}{2}$: 11 days) Siponimod (t $\frac{1}{2}$: 30 hours)	5 half-lives prior to Day 1* through the end of treatment
Rectal compounds	Rectal mesalamine, rectal corticosteroids	2 weeks prior to screening endoscopy through the end of treatment
Antidiarrheal agents**	Loperamide, diphenoxylate/atropine	2 weeks prior to screening endoscopy through the end of treatment
Other (non-biologic)	Cyclosporine (oral), thalidomide, tacrolimus, leflunomide, and any investigational agent	2 weeks prior to Day 1 through the end of treatment
Investigational biologics	Any investigational biologic agent	30 days prior to Day 1 (or at least 5 half-lives) through the end of treatment

*If subject has taken the concomitant medication within 5 half-lives prior to Day 1, but has an undetectable serum level on a commercially available assay assessed at screening, this is also acceptable for inclusion.

** Subjects who mistakenly use an antidiarrheal for a limited period of time (1 – 2 days) may be allowed to continue participation in the study following discussion and approval by the Medical Monitor and the Investigator.

If other prohibited concomitant medications, as shown in [Table 2](#) are taken by a subject prior to study participation or during the study, the Investigator must contact the Medical Monitor.

Table 2: Other Prohibited Concomitant Medications

Drug Class	Agents Disallowed	Prohibited Period
Other biologics	Fecal Microbiota Transplant (FMT), antibody based or other systemic biologics, eg, denosumab, trastuzumab	Requires Medical Monitor consultation

5.2.3 Allowed Concomitant Therapy

Concomitant medications for UC (i.e., oral probiotics, aminosalicylates, thiopurines, and/or oral corticosteroids) must be at stable doses 2 weeks prior to the screening endoscopy; a subject must be willing to maintain stable doses of these medications ^{CCI} [REDACTED] Oral prednisone or equivalent at doses ≤ 20 mg per day or budesonide ≤ 9 mg are permitted.

Low-dose aspirin for cardioprotection and/or temporary use of NSAID for minor ailments (other than for reasons related to the subject's underlying UC) may be used without prior consultation with the Medical Monitor.

The use of opioids related to the study procedure is allowed. Opioids used PRN should be assessed by the investigator on a case-by-case basis and upon consultation with the Medical Monitor.

5.2.3.1 Corticosteroid Tapering

A steroid taper should be initiated for responders at Week 12 of the IBT phase for subjects entering the CBT phase. For non-responders at Week 12 of the IBT phase, the steroid taper should be initiated at Week 24 of the OL phase only for subjects who have achieved a clinical response defined by the partial Mayo Score. The dose should be reduced at a rate starting at 2.5 mg per week up to 5 mg per week for prednisone (or equivalent taper if not prednisone) until the subject is no longer on steroids. Budesonide should be tapered by 3 mg every 2–3 weeks until the subject is no longer taking budesonide. For subjects undergoing steroid taper, steroids may be increased or restarted at doses up to and including their screening dose if return of symptoms is apparent. Subjects who are unable to steroid taper will be allowed to continue in the study. Subjects who need to increase their steroid dose beyond the maximum dose for allowed concomitant therapy use or increase their steroid treatment dose over their screening dose must be discontinued from the study.

5.3 Rescue Medications and Supportive Care

Sites will be staffed with medically trained personnel with appropriate access to full service acute-care hospitals to facilitate rapid institution of medical intervention.

See [Appendix 7](#) for specific DILI guidance and close observation recommendation around potential Hy's Law cases.

5.4 Treatment Compliance

Study drug administration will be performed by qualified and designated site staff and documented in source documents and the eCRF.

6 STUDY ACTIVITIES

6.1 Schedule of Events

Adverse events and concomitant medications will be recorded from randomization through the safety reporting period (see [Section 7.6.1.3](#)). Adverse events that are the result of study protocol-specified intervention (defined in [Section 7.6.1.1](#)) as well as any concomitant medications given for treatment of these adverse events, should be recorded from the time of informed consent. Schedules of events (SOEs) are provided in [Appendix 1](#). Descriptions of all study assessments are presented in [Section 7](#).

On applicable visits, all PRO and quality of life-related assessments must be completed prior to other study procedures.

6.2 Screening Visit

Documented, signed, and dated informed consent must be obtained by the Investigator or his/her designee prior to the performance of any study related procedures, including washout of prohibited medications. In regions where the legal age of consent is older than 18 years, informed consent must be obtained from and signed by both the subject and his or her legally acceptable representative, as applicable. A copy of the signed ICF must be given to the subject for their records.

After informed consent has been obtained, the subject has approximately 4 weeks (\pm 1 week) to complete all screening procedures. The subject's eligibility for the study will be evaluated during this period based on medical history, physical examination, laboratory values, Mayo Score diary data (SF and RB), and additional assessments, including screening endoscopy. Subjects who meet all of the inclusion and none of the exclusion criteria can be enrolled in the treatment period. For subjects eligible for this study, the randomization number is the same as the screening number.

Refer to [Appendix 1](#) for all the procedures to be performed during the Screening Period.

6.2.1 Screen Failure

A screen failure is defined as a subject who has provided informed consent and fails to meet the inclusion and/or exclusion criteria. Subjects who fail screening will not be randomized into the study nor receive study drug.

6.2.2 Rescreening of Subjects

Subjects may be rescreened once after consultation with the Medical Monitor. In these cases, a new screening number must be assigned for each subject rescreened. Rescreening should include all screening procedures listed in the SOEs (see [Table 3](#) and [Table 4](#)) unless noted otherwise and a new ICF must be signed to confirm ongoing consent for the study.

6.3 Initial Blinded Treatment Phase

6.3.1 Treatment Administration Visits

Eligible subjects will be randomized and receive their assigned SC dose of PT101 or placebo in a double-blind fashion starting on Day 1. Subjects will follow the schedule for dose administration and procedures for assessments as outlined in the SOEs (Table 3 and Table 4 in Appendix 1). The dose to be administered will be determined by the DRC and guided by the cohort progression criteria provided in Sections 3.1.1.4 and 9.3.4.

All safety, PK, and PD procedures are to be conducted prior to administration of study drug, unless otherwise specified. Subjects will be observed in clinic for 1 hour after administration of study drug.

6.3.2 Post-Dose Assessment Visits

Assessments will be performed post-dose to assess safety, PK, PD, biomarkers, and other outcomes. Subjects will follow the assessments as outlined in the SOEs (Appendix 1).

6.3.3 Early Termination Visit

Subjects who receive ≥ 1 dose of study drug should be encouraged to complete all study visits within the IBT phase. CCI

CCI visit will be asked to return to the study site for ET visit approximately 28 days of the last dose of study drug administration

CCI

6.3.4 End of Study Visit

For subjects who receive study drug and are not entering the CBT or OL phases CCI
CCI The site will conduct a follow-up phone call approximately 48 hours after the Day 85 visit to confirm no AEs related to Day 85 study procedures had occurred. Additionally, a follow-up call approximately 90 days after the final dose of PT101 will be conducted to assess any changes in UC disease status. Subjects will be asked whether their UC is active, whether they have experienced a UC flare (defined as period of active symptoms), and whether they have started a new therapy for UC.

If a subject decides to withdraw his or her consent for further participation after receiving study drug but before EOS, he/she may do so without penalty. All efforts will be made to follow the subject for safety until EOS.

6.4 Continued Blinded Treatment and Open Label Phases

At Week 12 (Day 85), eligibility for continuation in the CBT or OL phase will be determined by clinical response status (responders versus non responders) from the modified Mayo Score (using the endoscopic subscore derived by the Investigator).

6.4.1 Continued Blinded Treatment Phase

Subjects who are eligible to enter the CBT phase as described in Section 3.1.2 will receive their first dose of blinded study drug (same treatment allocation as in the IBT phase) on Day 85. [REDACTED] Assessments in this phase will primarily evaluate safety with exploratory efficacy assessments. [REDACTED]

[REDACTED] Subjects will have a safety follow-up visit approximately 28 days after their last dose of study drug. They will also receive a follow-up call approximately 90 days after the final dose of study drug to assess any changes in UC disease status. Subjects will be asked whether their UC is active, whether they have experienced a UC flare (defined as period of active symptoms), and whether they have started a new therapy for UC.

6.4.2 Open-Label Phase

Subjects who are eligible to enter the OL phase as described in Section 3.1.2 will receive their first dose of PT101 (there is no Placebo treatment arm in the Open-Label Phase) on Day 85. [REDACTED] Assessments in this phase will mainly assess safety and exploratory efficacy. [REDACTED] Subjects will have a safety follow-up visit approximately 28 days after their last dose of study drug. They will also receive a follow-up call approximately 90 days after the final dose of PT101 to assess any changes in UC disease status. Subjects will be asked whether their UC is active, whether they have experienced a UC flare (defined as period of active symptoms), and whether they have started a new therapy for UC.

6.5 Study Design/Dosing/Procedures Modifications Permitted Within Protocol Parameters

This is a Phase 1 assessment of PT101 in humans, and the PK, PD, and safety profiles of the compound are still being elucidated. This protocol is written with some flexibility to accommodate the inherent dynamic nature of Phase 1 clinical studies. Modifications to the dose, dosing regimen, and/or clinical or laboratory procedures currently outlined may be required to achieve the scientific goals of the study objectives and/or to ensure appropriate safety monitoring of the study subjects.

As such, some alterations from the currently outlined dose and/or dosing regimen may be permitted per DRC recommendation based on newly available data.

- Repeat of or decrease in the dose of the study drug administered in any planned cohort
- Lengthening of the time period between [REDACTED]

- Modification of the PK/PD sample processing and shipping details based on newly available data

7 STUDY ASSESSMENTS

7.1 Screening/Baseline Assessments

Only subjects who meet all eligibility criteria specified in [Section 4](#) will be enrolled in this study.

Subject medical history includes a thorough review of significant past medical history, current conditions, review of body systems, response to prior UC treatment, and any concomitant medications.

7.2 Response/Efficacy Assessments

7.2.1 Mayo Score

The Mayo Score is an instrument designed to measure disease activity in patients with UC. The Mayo Score ranges from 0 to 12 points and consists of the following 4 subscores, each graded from 0 to 3, with higher scores indicating more severe disease (see [Appendix 3](#)).

- Stool frequency (SF)
- Rectal bleeding (RB)
- Findings of flexible sigmoidoscopy
- Physician global assessment (PGA)

Calculation of the SF and RB subscores requires an assessment of the subject's bowel movement frequency and quantification of the amount of blood in the stool. The SF and RB Mayo subscores will be calculated based on the subject's Mayo Score diary data recorded in the week prior to the endoscopy (for modified Mayo Score) or prior to the visit (for partial Mayo Score) (see [Section 7.2.1.1](#) for eDiary instructions and review).

The mucosal appearance during the sigmoidoscopic/colonoscopic portion of the endoscopic examination will be assessed for calculation of the Mayo endoscopic subscore based on the scoring system provided in [Appendix 3](#). The endoscopic appearance will be read by both the Investigator and a central reader. Additional details are provided in the Central Imaging Management Solutions manual. Centrally read endoscopic subscores will be used for both IBT eligibility and the efficacy analyses. The Investigator-read endoscopic subscores will be used to assess eligibility for the OL and CBT phases.

The PGA subscore is assessed by the Investigator and is recorded at all study visits. The endoscopic subscore and the PGA must be performed by a physician qualified to perform

endoscopy. It is recommended that the same physician performs all such assessments for a particular subject throughout the study.

7.2.1.1 eDiary Instructions and Review

The SF and RB subscores are recorded daily in an eDiary. Subjects should be provided access to the eDiary and instructions for daily documentation of SF and RB. Additionally, all subjects will be provided with paper diary forms for cases where the subject doesn't have access to a suitable device for eDiary capture or as backup to the eDiary in case there is an issue with the subject's electronic device. Subjects should begin filling out the diary on the day of their initial screening visit and continue to fill it out on a daily basis throughout the remainder of the study. Subjects should be counseled about what is meant by normal SF: the average daily SF the subject experienced the last time the subject was in remission. If the subject has never been in remission, the normal SF is defined as the average daily SF before the initial onset of signs and symptoms of UC.

For the daily SF question, subjects should be counseled that a stool is defined as a visit to the toilet when they have either a bowel movement, pass blood only, pass mucus only, or pass blood and mucus. For the RB question, subjects should be counseled to select the category that describes their most severe RB over the last 24 hours. Subjects should be counseled to select "No Blood Seen" if they do not have a stool during a given day.

The modified Mayo Score will be used for the purposes of determining eligibility at screening and efficacy assessments at Week 12, the subscores for SF and RB will be calculated based on the data recorded in the diary for 3 consecutive days (excluding the bowel preparation day) during the week prior to the endoscopy. Thus, sites need to ensure subjects are entering eDiary (preferred) or paper diary forms data daily, especially prior to an endoscopy. Subjects must be instructed to document SF and RB on a daily basis and site personnel should be monitoring subject's compliance. For all subjects, the site will ensure that the SF and RB data are being entered in the eDiary or paper diary forms by the subject by conducting a follow up phone call within 3 days before the endoscopy bowel preparation day at Screening and Week 12.

The partial Mayo Score will be assessed throughout the study and be used at Week 24 for the subjects in the OL phase to determine if the subject can start steroid tapering (if applicable). The subscore for SF and RB will be calculated based on the data recorded in the diary on 3 days (no need to be consecutive days) during the week prior to the corresponding visit where the partial Mayo Score is assessed.

7.2.1.2 Endoscopy

A colonoscopy or flexible sigmoidoscopy will be performed and recorded for central reader review at Screening and Week 12 (or upon ET as applicable).

Screening endoscopies will occur as follows:

- Only in subjects with a RB subscore ≥ 1 , a SF subscore ≥ 1 and PGA ≥ 1 may proceed with screening endoscopy.

- Endoscopy (flexible sigmoidoscopy or colonoscopy) should be performed approximately 14 days prior to planned randomization to allow for Mayo endoscopic subscore calculation by the central reader to inform the modified Mayo Score utilized for eligibility (see inclusion criterion #3).
- Colonoscopy is required for:
 - Subjects > 50 years of age at screening if not performed within last 3 years
 - Subjects with extensive colitis ≥ 8 years, or disease limited to the left side of the colon for ≥ 10 years if not performed within 1 year before first administration of study drug

Week 12 endoscopies:

All subjects will have a flexible sigmoidoscopy at the end of the study or, if possible, at ET CCI

The Mayo endoscopic subscore will be provided to the Investigator or designated site staff by the vendor responsible for central reading. The value provided by the central reader will be used for calculation of the modified Mayo Score at screening and Week 12.

As SF and RB may be affected by bowel preparation for the endoscopy, the SF and RB subscores on the day prior to endoscopy, day of endoscopy, and day after endoscopy are not included in the calculation of the modified Mayo Score at screening and Week 12. For this reason, extended bowel preparation (> 24 hours prior to the procedure) is discouraged. Intestinal biopsies will be collected during endoscopy for efficacy assessments and exploratory biomarker analysis. At screening, up to 11 biopsies should be collected from the colon or sigmoid colon. At Week 12, up to 11 biopsies should be collected from the sigmoid colon. Please refer to the Lab Manual for specific collection instructions.

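### Screening biopsies may come from anywhere in the colon but Week 12 biopsies only from the sigmoid, so change in RHI, histologic response and the RHI part of UC-100 can partly reflect biopsy location

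*Protocol*

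**What the plan says.** Protocol 7.2.1.2 gives the biopsy site for each visit in adjacent sentences. For screening: "At screening, up to 11 biopsies should be collected from the colon or sigmoid colon". For Week 12: "At Week 12, up to 11 biopsies should be collected from the sigmoid colon". It leaves the detailed collection instructions to the Lab Manual.

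On the procedure, the section opens with "A colonoscopy or flexible sigmoidoscopy will be performed and recorded for central reader review at Screening and Week 12". For screening it repeats that either is allowed: "Endoscopy (flexible sigmoidoscopy or colonoscopy) should be performed approximately 14 days prior to planned randomization". Colonoscopy is mandatory for two groups. One is "Subjects > 50 years of age at screening if not performed within last 3 years"; the other is subjects with long-standing extensive or left-sided disease and no colonoscopy in the preceding year. For Week 12 the section then says "All subjects will have a flexible sigmoidoscopy at the end of the study or, if possible, at ET". That does not agree with the opening sentence, which names either procedure at both visits.

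The biopsies supply the Geboes score and the RHI. Protocol 2.2.3 and 7.2.3.2, with SAP Tables 5 and 6, list mean change in RHI, mean change in UC-100 (which contains the RHI) and histologic response (an RHI change of 7 points or more). All are exploratory endpoints. Protocol 9.3.4 reports them descriptively, separately for each dose level or regimen and for placebo.

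**The concern.** A change from baseline is interpretable as change in disease only if both values come from the same place. Here Week 12 is fixed to the sigmoid colon and screening is not. Inclusion criterion 5 shows that both extensive and left-sided colitis are expected, so inflammation may differ between segments within a subject. A subject biopsied outside the sigmoid at screening contributes an RHI change made of two parts: change over 12 weeks, and the difference between two sites.

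What is at stake is how the histology results are read. Efficacy results at Week 12 are among the data that inform selection of dose and regimen for later development (Protocol 9.3.4). Groups are small enough for a few mismatched subjects to move a group mean or response rate.

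**Working it through.** **1. Does anything in the two documents remove the mismatch?**
- Randomization is stratified by prior advanced therapy only (Protocol 3.1), not by procedure, disease extent or biopsy site.
- ANCOVA adjusts for the baseline value only (SAP 6.2.2.1). The Week 12 site is always sigmoid, so the site error sits in that baseline value.
- The two per-protocol sets are defined by corticosteroid use and by major deviations (SAP 4.2.3). A colonic biopsy at screening follows the protocol, so it is not a deviation.
- The only sensitivity analysis is per-protocol (SAP 6.2.5), and no subgroup analysis is planned (SAP 11).

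None of these addresses biopsy site.

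**2. Reproduce the instrument ranges** (Protocol Appendices 5 and 6)
- RHI = 1 x infiltrate + 2 x lamina propria neutrophils + 3 x epithelial neutrophils + 5 x erosion, each item 0 to 3. Maximum = 3 x (1 + 2 + 3 + 5) = 33, as stated.
- UC-100 = 1 + 16 x SF + 6 x MES + RHI. Maximum = 1 + 48 + 18 + 33 = 100, as stated. RHI supplies 33 of the 99 points of range, or one third.

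**3. What a site difference can do in one subject**
- One erosion level plus one lamina propria neutrophil level: 5 + 2 = 7 RHI points, equal to the histologic-response threshold.
- RHI has weight 1 in UC-100, so the same difference moves UC-100 by 7.
- If the screening site was the more inflamed, this looks like improvement. If it was the less inflamed, it hides improvement of the same size.

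**4. What it can do to a group mean.** The documents give neither the share of mismatched subjects nor the size of the difference, so both are assumptions. Shift in mean RHI change = share x 7, if all differences run the same way:

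| Share mismatched | Shift in mean RHI change |
|---|---|
| 10% | 0.10 x 7 = 0.7 |
| 25% | 0.25 x 7 = 1.75 |
| 50% | 0.50 x 7 = 3.5 |

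Differences in opposite directions would partly cancel in the mean but still add variance and misclassify individual responders.

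**5. What randomization leaves.** Site is fixed before randomization, so the expected share is the same in both arms. Chance imbalance was calculated as the probability that the two arms' mismatched shares differ by at least 25 percentage points, with independent binomial counts and the same true share:

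| True share | 8 vs 2 (one cohort) | 24 vs 6 (three cohorts pooled) |
|---|---|---|
| 10% | 34% | 9% |
| 25% | 68% | 25% |
| 50% | 63% | 32% |

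One subject is 1/8 = 12.5% of a PT101 group and 1/2 = 50% of a cohort's placebo group.

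**The case against.** The strongest reply is that the protocol defers to the Lab Manual for biopsy collection. That manual was not available and may already require sigmoid biopsies for histology at both visits. Screening biopsies also serve exploratory biomarker work, so the wider site wording may have been meant for those samples. This stands as a limit: the finding is that the protocol and SAP leave the site open, not that mismatched biopsies were taken. If the manual does fix the site, 7.2.1.2 should still say so, because its present wording permits otherwise.

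Two further replies are partly right. Randomization balances the mismatch in expectation, so there is no systematic bias in the PT101-placebo contrast. Pooling placebo across cohorts and adjusting for baseline both reduce the chance component. Neither repairs the within-arm changes or the response classification. Second, the endpoints are exploratory and descriptive, and the primary endpoint is safety; that limits the consequence.

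A reader might infer more than the documents support:
- **That scores will drift towards improvement.** Nothing says the screening site was usually the more inflamed one.
- **That the problem falls mainly on older or longer-duration subjects.** Colonoscopy is mandatory for them only without a recent one, and optional for everyone else.
- **That the Mayo endoscopic subscore (MES) is mismatched in the same way.** Protocol 7.2.1 does refer to "The mucosal appearance during the sigmoidoscopic/colonoscopic portion of the endoscopic" examination, but this can be read as naming the procedure used, and the Mayo item itself is named after flexible sigmoidoscopy. No text says a proximal or worst segment is scored. Change in MES is not an endpoint, and endoscopic improvement and remission use only the Week 12 value.

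**Conclusion.** The point holds for histology. As written, 7.2.1.2 allows screening and Week 12 biopsies from different segments, and nothing in the protocol or SAP corrects for it. Change in RHI, histologic response and the RHI third of the UC-100 range can partly reflect location, in either direction. A difference of two item levels is enough to reach the 7-point threshold in one subject. The group-level figures rest on assumed shares of 10% to 50% and an assumed 7-point difference in one direction; they show scale and are not estimates. Histologic remission and mucosal healing are unaffected, because they use Week 12 values only.

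For MES there is only a secondary question: whether the central reader scores the same segment at both visits. Baseline MES enters through change in modified and total Mayo (1 point per level), UC-100 (6 points per level) and clinical response. The item name suggests a consistent sigmoid reading, and the imaging manual, also not available, may settle it.

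**What to change.** 1. State in Protocol 7.2.1.2 that the biopsies used for Geboes and RHI are taken from the sigmoid colon at screening, as at Week 12, whichever procedure is used. Align the Lab Manual, or cite it if it already says this.
2. Reconcile the opening sentence of 7.2.1.2, which names either procedure at Week 12, with the later sentence that "All subjects will have a flexible sigmoidoscopy at the end of the study".
3. For subjects already enrolled, use the recorded biopsy site where available. Add to the SAP a sensitivity summary of RHI change, UC-100 change and histologic response in subjects with matched sites. SAP 14 places finalization before the final database lock, which leaves room to prespecify it.
4. Confirm with the central reading vendor that MES is scored on the same segment at both visits. Restricting the screening MES by a new rule is a separate decision, because it could change who qualifies under inclusion criterion 3; it is not needed for this fix.

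The cost is a sentence in the protocol, a check of two manuals and one extra set of descriptive tables. No procedure or biopsy is added. The matched-site summary will rest on fewer subjects in groups that are already small, and the site may not be retrievable for everyone.
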